12.1.6 Suspected transmission of an infectious agent via a medicinal product

For the purposes of reporting, any suspected transmission of an infectious agent via a medicinal product should be considered as an SAE; such cases must be reported immediately, recorded in the AE module of the eCRF, and followed as any other SAE. Any organism, virus, or infectious particle (eg, prion protein transmitting transmissible spongiform encephalopathy), pathogenic or nonpathogenic, is considered an infectious agent.

12.1.7 Overdose of investigational medicinal product

Excessive dosing (beyond that prescribed in the protocol and including overdose) should be recorded in the eCRF. Any SAE or nonserious AE associated with excessive dosing must be followed as any other SAE or nonserious AE. These events are only considered AEs or SAEs if there are associated clinical signs and symptoms or if the act of taking the excess medicine itself is an AE or SAE (eg, suicide attempt).

12.1.8 Safety signal detection

Selected data from this study will be reviewed periodically to detect as early as possible any safety concern(s) related to the IMP so that Investigators, clinical study subjects, regulatory authorities, and IRBs will be informed appropriately and as early as possible.

The Study Physician or medically qualified designee/equivalent will conduct an ongoing review of SAEs and perform ongoing SAE reconciliations in collaboration with the PS representative.

As appropriate for the stage of development and accumulated experience with the IMP, medically qualified personnel at UCB may identify additional safety measures (eg, AEs, vital signs, laboratory or electrocardiogram [ECG] results) for which data will be periodically reviewed during the course of the study.

12.2 Laboratory measurements

The following laboratory parameters will be measured as outlined in the Schedule of Study Assessments (Table 5-1):

Table 12–1: Laboratory measurements

Hematology	Chemistry	Urinalysis
Basophils	Calcium	Albumin
Eosinophils	Chloride	Bacteria
Lymphocytes	C-reactive protein	Crystals
Atypical lymphocytes	Magnesium	Glucose
Monocytes	Potassium	pH
Neutrophils	Sodium	RBC
Hematocrit	Glucose	WBC
Hemoglobin	BUN	Urine dipstick for pregnancy testing ^a
MCH	Creatinine	
MCHC	ALP	
MCV	AST	
Platelet count	ALT	
RBC count	GGT	
WBC count	Total bilirubin	
	LDH	
	Total cholesterol	
	Albumin	
	Beta-D-glucan	
	Sialylated carbohydrate antigen KL-6	
	Hepatitis B surface antigen ^b	
	Hepatitis B core antibody ^{b,c}	
	Hepatitis B surface antibody ^{b,c}	
	Hepatitis type B virus DNA ^c	
	Hepatitis type C virus antibody ^b	
	Human immunodeficiency virus antigen ^b	
	Human immunodeficiency virus antibody ^b	
	T-cell lymphotropic virus type-1 antibody ^b	
	Serum pregnancy testing ^a	

ALP=alkaline phosphatase; ALT=alanine aminotransferase; AST=aspartate aminotransferase; BUN=blood urea nitrogen; DNA=deoxyribonucleic acid; GGT=gamma-glutamyltransferase; HBc=hepatitis type C virus; HBs=hepatitis B surface; HBV=hepatitis type B virus; LDH=lactate dehydrogenase; MCH=mean corpuscular hemoglobin; MCHC=mean corpuscular hemoglobin concentration; MCV=mean corpuscular volume; RBC=red blood cell; SFU=Safety Follow-Up; WBC=white blood cell

^a Pregnancy testing will consist of serum testing at Screening. The pregnancy test will be urine at all other visits.

^b Performed at Screening only

^c If the subject is either HBs antibody-positive or HBc antibody-positive at Screening, quantitative measurement of HBV-DNA should be performed every 4 weeks from Baseline to Week 52 and at SFU.

12.2.1 Evaluation of PDILI

The PDILI IMP discontinuation criteria for this study are provided in Section 6.3.1, with the accompanying required follow-up investigation and monitoring detailed below. All PDILI events must be reported as an AE and reported to the study site and Sponsor within 24 hours of learning of their occurrence. Any PDILI event that meets the criterion for potential Hy's Law must be reported as an AE of special interest (see Section 12.1.1.3), and, if applicable, also reported as an SAE (see Section 12.1.1.2).

Evaluation of PDILI consists of the diagnostic testing and continued monitoring included in Table 12-2 (specific tests dependent on laboratory results and corresponding symptoms) and consultation with a local hepatologist (if applicable; discussed in Section 12.2.1.1). The local hepatologist is the expert usually consulted by the treating physician for assessment and management of potential hepatic disease. This would usually be a hepatologist, but may be a gastroenterologist. Additional investigation and monitoring may be required and adapted based on the diagnosis after the cause of the liver injury/abnormality is confirmed (details in Section 12.2.1.4).

The results of all monitoring, including laboratory testing and other testing, should be made available to the study site and Sponsor.

All initial tests resulting in abnormal hepatic laboratory values need to be repeated, but appropriate medical action must not be delayed waiting for the repeat result.

If tests are done locally for more rapid results, a concurrent sample should also be sent to the central laboratory whenever possible. Medical care decisions are to be made initially using the most rapidly available results and a conservative approach must be taken if the results from the 2 laboratory tests are significantly different. Data from the local and central laboratory are to be recorded on the applicable eCRF pages.

When IMP is discontinued, all concomitant medications and herbal supplements that are not medically necessary should also be discontinued. In these cases, the Investigator should also consider dose reduction for medically necessary concomitant medication and consider changing any medically required concomitant medication known to be hepatotoxic to a suitable alternative.

Rechallenge with a substance potentially causing drug-induced liver injury is dangerous, may be fatal, and must not occur.

The table below summarizes the approach to investigate PDILI.

Table 12–2: Required investigations and follow up for PDILI

Laboratory value			Immediate		Follow up	
ALT or AST	Total bilirubin	Symptoms ^a of hepatitis or hypersensitivity	Consultation requirements	Actions	Testing	Evaluation
≥3xULN	≥2xULN ^b	NA	Hepatology consult. ^c	Immediate, permanent IMP discontinuation.	Essential: Must have repeat liver chemistry values and additional testing completed ASAP (see Section 12.2.1.3); recommended to occur at the site with HCP.	Monitoring of liver chemistry values at least twice per week until values normalize, stabilize, or return to within baseline values. ^d
≥8xULN	NA	NA	Medical Monitor must be notified within 24 hours (eg, by laboratory alert) and subject discussed with Medical Monitor ASAP.			
≥3xULN	NA	Yes		Immediate, temporary or permanent, IMP discontinuation.		
≥3xULN (and ≥2x baseline) and <5xULN	<2xULN	No	Discussion with Medical Monitor required if the criterion that allows for IMP continuation is met.	Further investigation > immediate IMP discontinuation not required (see Section 12.2.1.2).	Not required unless otherwise medically indicated (at discretion of Investigator).	

Table 12–2: Required investigations and follow up for PDILI


≥5xULN (and ≥2x baseline) and <8xULN
	
<2xULN
	
No
	
Hepatology consult if there is no evidence of resolution (see Follow up requirements).^c
 
Discussion with Medical Monitor required.
	
IMP discontinuation required if any of the following occur:
 
 • Subject cannot comply with monitoring schedule. • Liver chemistry values continue to increase during 2 week monitoring period. • Liver chemistry values remain ≥5xULN (and ≥2x baseline) after 2 week monitoring period. 	
Essential: Every attempt must be made to have repeat liver chemistry values and additional testing completed within 48 hours at the site with HCP (see Section 12.2.1.3).
	
Monitoring of liver chemistry values at least twice per week for 2 weeks.^d
 
 • Immediate IMP discontinuation required if liver chemistry values continue to increase. 
After 2 weeks of monitoring liver chemistry values:
 
 • Discontinue IMP if levels remain ≥5xULN (and ≥2x baseline); monitor until values normalize, stabilize, or return to within baseline values.^d • Continue IMP if levels are no longer ≥5xULN (and ≥2x baseline); continue to monitor at least twice per week until values normalize, stabilize, or return to within baseline values.^d
--	------------------	-----------	--	---	--	---

ALP=alkaline phosphatase; ALT=alanine aminotransferase; ASAP=as soon as possible; AST=aspartate aminotransferase; HCP=healthcare practitioner; IMP=investigational medicinal product; NA=not applicable; PDILI=potential drug-induced liver injury; ULN=upper limit of normal

^a Hepatitis symptoms include fatigue, nausea, vomiting, and right upper quadrant pain or tenderness; hypersensitivity symptoms include eosinophilia (>5%), rash, and fever (without clear alternative cause).

^b If the subject also has ≥2xULN ALP, the possibility of an indication of biliary obstruction should be discussed with the Medical Monitor.

^c Details provided in Section 12.2.1.1. The local hepatologist is the expert usually consulted by the treating physician for assessment and management of potential hepatic disease. This would usually be a hepatologist, but may be a gastroenterologist.

^d Unless an alternative monitoring schedule is agreed by the Investigator and UCB responsible physician. Determination of stabilization is at the discretion of the Investigator in consultation with the hepatologist (as applicable) and UCB responsible physician, as needed.

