6.3.1 Potential drug-induced liver injury IMP discontinuation criteria

Subjects with potential drug-induced liver injury (PDILI) must be assessed to determine if IMP must be discontinued. In addition, all concomitant medications and herbal supplements that are not medically necessary should also be discontinued.

The PDILI criteria below require immediate and permanent discontinuation of IMP:

- Subjects with either of the following:
 - ALT or AST \geq 8xULN
 - ALT or AST \geq 3xULN and coexisting total bilirubin \geq 2xULN

The PDILI criterion below requires immediate discontinuation of IMP:

- Subjects with ALT or AST \geq 3xULN who exhibit temporally associated symptoms of hepatitis or hypersensitivity. Hepatitis symptoms include fatigue, nausea, vomiting, right upper quadrant pain or tenderness. Hypersensitivity symptoms include fever (without clear alternative cause), rash, or eosinophilia (ie, $>$ 5%).

The PDILI criterion below allows for subjects to continue on IMP at the discretion of the Investigator.

- Subjects with ALT or AST \geq 3xULN (and $>$ 2x baseline) and $<$ 8xULN, total bilirubin $<$ 2xULN, and no eosinophilia (ie, \leq 5%), with no fever, rash, or symptoms of hepatitis (eg, fatigue, nausea, vomiting, right upper quadrant pain or tenderness).

Evaluation of PDILI must be initiated as described in [Section 12.2.1](#). If subjects are unable to comply with the applicable monitoring schedule, IMP must be discontinued immediately.

Investigators should attempt to obtain information on subjects in the case of IMP discontinuation to complete the final evaluation. Subjects with PDILI should not be withdrawn from the study until investigation and monitoring are complete. All results of these evaluations and observations, as well as the reason(s) for IMP discontinuation and subject withdrawal (if applicable), must be recorded in the source documents. The CRF must document the primary reason for IMP discontinuation.

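### Protocol 12.2.1 forbids rechallenge after suspected drug-induced liver injury, yet its own Table 12-2 permits a temporary stop for symptomatic cases, and no passage says whether or when that stop may end.

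*Protocol*

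**What the plan says.** Three places in the protocol govern stopping study drug for potential drug-induced liver injury (PDILI).

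- **Section 12.2.1, running text.** "Rechallenge with a substance potentially causing drug-induced liver injury is dangerous, may be fatal, and must not occur". No exception is attached. The same section says that the discontinuation criteria are those in 6.3.1 and that 12.2.1 supplies the follow-up.
- **Section 6.3.1.** Two criteria (ALT or AST of at least 8xULN; or at least 3xULN with bilirubin of at least 2xULN) fall under "The PDILI criteria below require immediate and permanent discontinuation of IMP". The criterion of at least 3xULN with symptoms falls under "The PDILI criterion below requires immediate discontinuation of IMP", with nothing about permanence. For asymptomatic values from 3 to below 8xULN with bilirubin below 2xULN, the lead-in is "The PDILI criterion below allows for subjects to continue on IMP at the discretion of the Investigator".
- **Table 12-2.** For at least 3xULN with symptoms the action is "Immediate, temporary or permanent, IMP discontinuation". The asymptomatic range is split at 5xULN. In the upper row (5 to below 8xULN) the action is "IMP discontinuation required if any of the following occur", followed by three triggers: the subject cannot keep to the monitoring schedule, values go on rising during the 2-week monitoring period, or values are still at least 5xULN and at least 2x baseline when it ends.

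Section 12.2.1.2 refers to 6.3.1 and Table 12-2 together for the immediate action and does not say which prevails.

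**The concern.** A stop that can never be lifted is not temporary. By listing a temporary stop, Table 12-2 suggests that some symptomatic subjects may resume dosing, and 6.3.1 points the same way by reserving permanence for its other two criteria. The rechallenge sentence in 12.2.1 points the other way, about an event that it describes as possibly fatal. An investigator with a recovering subject finds no condition, interval or finding that settles whether dosing may resume.

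The second issue is where the rules are written. An investigator who goes to 6.3.1, as 12.2.1 directs, reads that continuation between 3 and 8xULN is discretionary and does not see two stops that Table 12-2 makes mandatory.

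With approximately 35 planned sites (Protocol 5.1.4), similar events could be handled differently. The status of the stop also feeds the outputs. SAP 10.2 tabulates adverse events that led to permanent discontinuation of study drug. SAP 8.3.5 censors time to PASI response at study drug discontinuation. SAP 10.1.2 ignores dosing gaps in the final exposure derivations. A subject who stops and restarts is therefore counted differently from one who stops for good.

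**Working it through.** There is no figure to reproduce and no arithmetic applies. The check is a comparison of the current text, region by region.

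| Finding | Section 6.3.1 | Table 12-2 | Section 12.2.1 text | Result |
|---|---|---|---|---|
| At least 8xULN, or at least 3xULN with bilirubin at least 2xULN | Immediate, permanent stop | Immediate, permanent stop | No rechallenge | Agree |
| At least 3xULN with symptoms | Immediate stop, permanence not stated | Immediate stop, temporary or permanent | No rechallenge, no exception | Restart unresolved |
| 3 to below 5xULN, no symptoms, bilirubin below 2xULN | Continuation at discretion | Immediate stop not required | Not addressed | Compatible |
| 5 to below 8xULN, no symptoms, bilirubin below 2xULN | Continuation at discretion | Stop mandatory on any of three triggers | Not addressed | Two triggers missing from 6.3.1 |

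**Row 2.** Table 12-2 and 6.3.1 are consistent with each other: both keep permanence for the first row. The conflict is between that pair and the rechallenge sentence. Two things could remove it: a statement that a restart under given conditions is not rechallenge, or a statement that no restart follows. Neither is in 6.3.1, 12.2.1, Table 12-2 or 12.2.1.2. The protocol does write such conditions elsewhere. For new latent tuberculosis, Section 12.6 gives an earliest time for resuming study drug and requires discussion with the Medical Monitor.

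**Row 4.** Of the three triggers, inability to comply with monitoring is also in 6.3.1, and the two places agree. Continued rise, and persistence at or above 5xULN (and 2x baseline) after 2 weeks, are in Table 12-2 only. Both arise after the initial decision to continue, during monitoring that 6.3.1 itself requires by sending the reader to 12.2.1. A site can therefore obey both texts: continue at first, monitor, and stop if a trigger occurs. What fails is the statement in 12.2.1 that the criteria are in 6.3.1, because two of them are not.

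**Statistical reach.** The sample size in Protocol 14.8.1 rests on assumed PASI75 rates, allocation and alpha. The primary model in SAP 8.1.2 uses treatment group and prior biologic exposure. Neither takes an input from the liver rules.

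**The case against.** The strongest defence of the restart rule is that the ban covers only a drug that may have caused the injury. Section 12.2.1.3 requires testing to find or exclude another cause, and 12.2.1 allows for management to change once a cause is confirmed. On that view a temporary stop lasts until the study drug is cleared, and a later restart is not rechallenge. This is plausible, but no current passage says it. The table row concerns potential drug-induced injury by definition, so a site would have to supply the exception itself.

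Three stronger readings are tempting, and the documents do not support them.

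- *That 6.3.1 and Table 12-2 contradict each other at 5 to below 8xULN.* They do not. The table's extra stops come later in time, 6.3.1 refers on to 12.2.1, and 12.2.1.2 tells the reader to use both places.
- *That the baseline multiple differs, strictly above 2x in 6.3.1 and at least 2x in the table.* The strict sign appears once, in the extracted text of 6.3.1. The Amendment 2 log prints the same sentence twice with the non-strict sign, and Amendments 3 and 4 list no change to it. A misread symbol is the likelier explanation, and the difference would matter only at exactly twice baseline. It is not part of this point.
- *That sites may simply choose a text, and that every subject with such a value is affected.* Section 12.2.1.1 requires that the Medical Monitor be notified within 24 hours and that the subject be discussed as soon as possible. The gaps reach only symptomatic subjects considered for restart, and asymptomatic subjects whose values keep rising or stay high after 2 weeks.

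**Conclusion.** The point holds for the symptomatic criterion. A temporary stop and an unqualified ban on rechallenge stand in the same section, and nothing states whether or when the stop may end. This rests on current text alone and on taking a temporary stop to imply a possible restart. The 5 to below 8xULN matter is secondary: 6.3.1 is incomplete against the role that 12.2.1 gives it, but the two texts can be followed together.

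The size cannot be put in numbers, because the documents give no expected frequency of these events. There is no effect on the sample size or the primary test. The effect is on uniform safety handling and on whether a stop is recorded as temporary or permanent, which carries into the SAP outputs on adverse events, censoring and exposure. It merits correction on safety grounds despite the small statistical reach.

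**What to change.** The sponsor should reconcile Protocol 6.3.1, the text of 12.2.1, Table 12-2 and 12.2.1.2 on two matters.

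1. Restart after the stop for symptomatic ALT or AST of at least 3xULN. The rechallenge sentence, the table entry and the 6.3.1 criterion should give one answer on whether a stop may be temporary and, if it may, on what stated conditions it ends.
2. The mandatory stops for asymptomatic 5 to below 8xULN. They should appear, or be expressly referred to, in the section that is said to hold the discontinuation criteria, and it should be clear how 6.3.1 and Table 12-2 are to be read together.

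Which clinical rule is right is for the sponsor and its medical advisers; this review proposes none. The cost is protocol wording. Sample size and the primary analysis are unchanged.

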12.2.1.1 Consultation with Medical Monitor and local hepatologist

Potential drug-induced liver injury events require notification of the Medical Monitor within 24 hours (eg, by laboratory alert), and the subject must be discussed with the Medical Monitor as soon as possible. If required, the subject must also be discussed with the local hepatologist. The local hepatologist is the expert usually consulted by the treating physician for assessment and management of potential hepatic disease. This would usually be a hepatologist, but may be a gastroenterologist. If determined necessary, this discussion should be followed by a full hepatology assessment (see Section 12.2.1.3) and SAE report (if applicable).

12.2.1.2 Immediate action: determination of IMP discontinuation

All PDILI events require immediate action, testing, and monitoring.

The immediate action is dependent on the laboratory values and symptoms of hepatitis or hypersensitivity and ranges from continuation of IMP (followed by immediate investigation) to immediate and permanent discontinuation (see Section 6.3.1 and Table 12-2 for details).

When IMP is discontinued, all concomitant medications and herbal supplements that are not medically necessary should also be discontinued. The Investigator should also consider dose reduction for medically necessary concomitant medication and consider changing any medically required concomitant medication known to be hepatotoxic to a suitable alternative.

12.2.1.3 Testing: identification/exclusion of alternative etiology

The measurements and additional information required for the assessment of PDILI events when there is a reasonable possibility that they may have been caused by the IMP are detailed in Table 12-3 (laboratory measurements) and Table 12-4 (additional information). Results of the laboratory measurements and information collected are to be submitted to the Sponsor on the corresponding eCRF. If the medical history of the subject indicates a requirement for other assessments not included below, these additional assessments should be completed and submitted, as applicable.

All blood samples should be stored, if possible. If tests are done locally for more rapid results, a concurrent sample must also be sent to the central laboratory.

The following measurements are to be assessed:

Table 12–3: PDILI laboratory measurements

Virology-related	Hepatitis A IgM antibody
	HBsAg
	Hepatitis E IgM antibody
	HBcAb-IgM
	Hepatitis C RNA
	Cytomegalovirus IgM antibody
	Epstein-Barr viral capsid antigen IgM antibody (if unavailable, obtain heterophile antibody or monospot testing)
Immunology	Anti-nuclear antibody (qualitative and quantitative)
	Anti-smooth muscle antibody (qualitative and quantitative)
	Type 1 anti-liver kidney microsomal antibodies (qualitative and quantitative)
Hematology	Eosinophil count
Urinalysis	Toxicology screen
Chemistry	Amylase
	If total bilirubin $\geq 1.5 \times \text{ULN}$, obtain fractionated bilirubin to obtain % direct bilirubin
	Serum CPK and LDH to evaluate possible muscle injury causing transaminase elevation
Additional	Prothrombin time/INR ^a
	Serum pregnancy test
	PK sample

ALT=alanine aminotransferase; CPK=creatine phosphokinase; HBcAb-IgM=hepatitis B core antibody-IgM; HBsAg=hepatitis B surface antigen; IgM=immunoglobulin M; INR=international normalized ratio; LDH=lactate dehydrogenase; PDILI=potential drug-induced liver injury; PK=pharmacokinetic; RNA=ribonucleic acid; ULN=upper limit of normal

^a Measured only for subjects with ALT $> 8 \times \text{ULN}$, elevations in total bilirubin, and symptoms of hepatitis or hypersensitivity. Hepatitis symptoms include fatigue, nausea, vomiting, and right upper quadrant pain or tenderness; hypersensitivity symptoms include eosinophilia ($> 5\%$), rash, and fever (without clear alternative cause).

The following additional information is to be collected:

Table 12–4: PDILI information to be collected

New or updated information
Concomitant prescription and over-the-counter medications (eg, acetaminophen, herbal remedies, vitamins); dosages and dates should be included.

Table 12–4: PDILI information to be collected

New or updated information

Pertinent medical history, including the following:
 
 History of liver disease (eg, autoimmune hepatitis, nonalcoholic steatohepatitis or other “fatty liver disease”) Adverse reactions to drugs Allergies Relevant family history or inheritable disorders (eg, Gilbert’s syndrome, alpha-1 antitrypsin deficiency) Recent travel Progression of malignancy involving the liver (Note: Metastatic disease to the liver, by itself, should not be used as an explanation for significant AST and/or ALT elevations.)
The appearance or worsening of clinical symptoms of hepatitis or hypersensitivity (eg, fatigue, nausea, vomiting, right upper quadrant pain or tenderness, decreased appetite, abdominal pain, jaundice, fever, or rash)
Recent clinically significant hypotension or hypoxemia with compromised cardiopulmonary function
Alcohol and illicit drug use
Results of liver imaging or liver biopsy, if done
Results of any specialist or hepatology consult, if done
Any postmortem/pathology reports

ALT=alanine aminotransferase; AST=aspartate aminotransferase; PDILI=potential drug-induced liver injury

